A Blinded Evaluation of the Effectiveness and Efficacy of the MyHealthyPregnancy Application Statistical Analysis Plan

This study will evaluate the effectiveness and efficacy of the MyHealthyPregnancy App, an app designed to reduce preterm birth risk. This study will use observational cohort data collected at the University of Pittsburgh Medical Center between September of 2019 and February of 2022.

July 18, 2022

[name], [name]

1. Description of the study

MyHealthyPregnancy (MHP) was developed using decision science principles to help prevent preterm birth. An observational cohort trial was conducted at the University of Pittsburgh Medical Center starting in September of 2019 until February 2022. This trial compares the effectiveness of MHP to usual care for pregnant people who delivered at the University of Pittsburgh Medical Center (UPMC). Patients at UPMC were able to download the MHP app after receiving a prescription for the app, as indicated by an EHR variable. Those who were prescribed the app and downloaded it were in the *MHP cohort*. Those who were prescribed the app and did not download it were in the *usual care cohort*. Prescriptions were offered to pregnant people by their care team at an early prenatal visit at UPMC.

EHR data is available for both cohorts of patients. It is the source of all measures, unless otherwise noted.

A linear effects model will be used to evaluate effectiveness by estimating the average treatment effect for the primary endpoint, preventing preterm birth risk.

For each dependent measure, these models will control for primary predictors, as identified in the research literature, that are available in the EHR.

A dose-response model will be used to estimate the effects of continuous measures of non-adherence (as opposed to dichotomous non-adherence, such as not initiating app use). Multiple measures of adherence will be analyzed, including measures of daily use, weekly use, time to initiation, and time from discontinuation to birth.

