1.1. Principal research objectives

1.1.1. Primary objective

To compare gestational weeks at birth, for the MyHealthy Pregnancy (MHP) cohort, defined as pregnant people who downloaded the MyHealthyPregnancy app, thereby onboarding into the study, compared to the usual care cohort, defined as pregnant people, who were invited to download the app, but did not do so. Analyses control for predictors of preterm birth.

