1.3. Method of allocation of groups

Participants seeking prenatal care at the UPMC were offered a prescription to download the MyHealthyPregnancy app during an early prenatal visit. Participants were prescribed the app by

¹ Gestational weight gain will be evaluated based on 2009 Institute of Medicine guidelines (11). Recommended gestational weight gain depends on pregravid BMI and if it is a singleton or multiple pregnancy.

their obstetrician or the EHR system and had the option of downloading the app and consenting to trial participation. We have no direct knowledge of how obstetricians decided whether to offer the prescription or if there was encouragement to download the app in addition to the automated EHR prescription. Participants who downloaded the app will be categorized as the MyHealthyPregnancy (MHP) cohort. Participants who did not download the app will be categorized as the usual care cohort.

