2.3. Treatment Usage

At its current stage of development, the MHP app does not prescribe a set dosage, specifying how often patients should interact with it in order to have desired effects. As such, this study investigates app usage as a mediator of the outcome, rather than comparing users who did and did not meet a predetermined dosage.

We will assess the following aspects of usage: how soon after receiving the prescription participants initiated app use (in days); how soon they discontinued app use prior to delivery (in days since initiation); the percentage of days they used it overall (within the usage period); and the percentage of weeks they used it at least once (within the usage period). See Appendix A for details on these use metrics.

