2.4. Loss to follow-up and other missing data

Given data-sharing constraints with UPMC, outcome data is available only for participants who delivered at UPMC hospitals. LH will report how many people downloaded the app and did not deliver at UPMC. This will allow us to estimate the percentage of participants lost due to delivering out of the system.

For included participants, there is a very little missing data for the primary measure (80/13752=0.06%). We will assume that such data is missing at random and exclude participants whose data is missing for a measure from analyses involving that measure. There is no missing data for the secondary measures. The same practice will be followed for the exploratory outcomes. No imputation will be done for any outcome measures.

Missing categorical values for baseline covariates (baseline disease information and demographics) will not be imputed, but treated as an additional category. Continuous variables missing less than 5% of the data will be imputed with the median value for that variable. Two continuous baseline covariates are missing more than 5% of data ADI_NATRANK (1330/13752=9.7%) and PREGRAVID_WEIGHT (1318/13752=9.6%). For these two variables, scatterplots and Little's test will be used to investigate if the data is missing completely at random (MCAR), missing at random (MAR), or missing not at random (MNAR) on 20% of the unblinded data. If the data appears to be MCAR or MNAR, median imputation will be used. If the data is MAR, multiple imputation will be used. If multiple imputation is needed, LH will generate data for the missing values so that EG remains blinded. For all missing data, we will conduct

sensitivity analyses, repeating analyses of primary and secondary outcomes using imputed values two standard deviations above and below the median. See Appendix A for the full list of collected baseline covariates.

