3.1. Main analyses of treatment differences

The main analysis compares the mean gestational weeks at birth between the MHP and usual care cohorts. An estimate of the average treatment effect, 95% confidence interval, and effect size will be reported. EG will remain blind to the 80% of outcome data not used to set the terms of the analysis (Section 2.5).

The primary and secondary outcomes will be evaluated at the 5% significance level. No correction for chance will be used for the primary outcome, as there is only one test. For the 9 secondary outcomes, we will report both corrected and uncorrected p-values, using the Bonferroni correction to reduce risk of reporting a false positive result. As a sensitivity analysis, the Bonferroni corrected p-values for ten outcome values will be reported in the supplemental material of the report.

All tests will include all participants with data on the outcome measure involved.

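### Cohorts are set by ever/never download with no time limit, so late downloads could bias gestational age towards MHP, and no planned analysis corrects this

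*SAP*

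**What the plan says.** **Cohort assignment.** Section 1 says "Those who were prescribed the app and did not download it were in the" usual care cohort. Section 1.1.1 describes that cohort as "pregnant people, who were invited to download the app, but did not do so", and section 1.3 repeats the rule: "Participants who did not download the app will be categorized as the usual care cohort". Eligibility (section 1.4.1) sets no download deadline and no gestational-age limit. The one timing statement concerns the prescription: participants "were offered a prescription to download the MyHealthyPregnancy app during an early prenatal visit" (section 1.3).

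**Primary comparison.** Section 3.1: "The main analysis compares the mean gestational weeks at birth between the MHP and usual care cohorts". Preterm birth is secondary outcome 1.

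**Timing of use.** Section 2.3 plans to assess "how soon after receiving the prescription participants initiated app use (in days"). Section 1 adds: "Multiple measures of adherence will be analyzed, including measures of daily use, weekly use, time to initiation, and time from discontinuation to birth". Section 3.1.4 then names only daily and weekly usage, with an optional cooperativity index, for the dose-response models.

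**Bias control.** Sections 3.1.1 and 3.1.5 plan regression on baseline confounders, propensity matching, inverse probability of treatment weighting, and a sensitivity analysis that adds the date of the first prenatal visit.

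**The concern.** Exposure is classified after follow-up has begun, on an outcome that is itself a time. Someone who would have downloaded at week 37 but delivers at week 35 is counted as usual care. Someone who does download at week 37 cannot have delivered preterm. With no app effect at all, this moves some short pregnancies into usual care and guarantees a minimum length for each late downloader in MHP. This is immortal-time bias.

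The design is sensitive to small shifts. The SAP puts the difference detectable with 80% power at 0.51 day, so an artefact of a fraction of a day can raise the false-positive rate of the primary test.

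**Working it through.** **1. Reproduce the SAP's figure.** Inputs from section 1.5: cohorts of 7147 and 5197 (labels blinded, so MHP is 57.9% or 42.1% of 12,344) and SD 10 days. The 5% level in section 3.1 is taken as two-sided.

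SE = 10 × √(1/7147 + 1/5197) = 0.182 day. Detectable difference = 2.8016 × 0.182 = 0.51 day, as stated.

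**2. Bias under no app effect.** Let p be the share intending to download, q the share of those who would do so late, T the intended late download time and g gestational age at birth. Assume that intention and delay are unrelated to g. An intending person ends up in MHP with probability S(g) = 1 − q·P(T > g). With m the mean of S and C = Cov(g, S), the MHP mean is raised by C/m and the usual care mean is lowered by pC/(1 − pm). Hence

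bias = C / [m(1 − pm)].

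**3. Assumed timing (not in the SAP).** Prescription at week 10 (day 70), most downloads within 14 days, late ones spread evenly from day 84 to a last day E, and g Normal(275, 10). Then C = 100·q·Φ((E − 275)/10)/(E − 84).

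For E = 280 (week 40) and q = 0.30:
- C = 100 × 0.30 × 0.6915/196 = 0.1058
- mean of (280 − g) where positive = 10 × (0.3521 + 0.5 × 0.6915) = 6.98 days, so m = 1 − 0.30 × 6.98/196 = 0.989
- p = 0.579: 0.1058/(0.989 × 0.427) = +0.25 day
- p = 0.421: 0.1058/(0.989 × 0.583) = +0.18 day

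The rejection rate of a nominal 5% test is Φ(−1.96 − b/SE) + 1 − Φ(1.96 − b/SE), with b the bias and SE the unadjusted 0.182.

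| Late share | 58% intend: bias (day), rejection | 42% intend: bias (day), rejection |
|---|---|---|
| 10% | +0.08, 7% | +0.06, 6% |
| 20% | +0.17, 15% | +0.12, 10% |
| 30% | +0.25, 28% | +0.18, 17% |

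In these rows about 4%, 8% or 12% of MHP downloads fall after week 28. Simulation (6 million deliveries per scenario) agrees.

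**4. Dependence on the last download week** (30% late, SD 10, 58%/42% intending). Week 36: C = 100 × 0.30 × Φ(−2.3)/168 = 0.0019, so the bias is below 0.005 day in both cases. Week 38: 0.07/0.05 day. Week 40: 0.25/0.18 day.

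**5. Other assumptions, by simulation.**
- Heavier preterm tail (92.5% N(276.5, 8.5) + 7.5% N(246, 24); SD 13.2, 7.1% preterm), downloads to week 40: +0.18, +0.36, +0.53 day at 58% and +0.13, +0.26, +0.39 day at 42%, for 10%, 20%, 30% late.
- Preterm birth is falsely lower in MHP by about 0.1 to 0.85 percentage points across both distributions.
- Exponential delay, across both distributions and both shares: mean 14 days, 0.00; 30 days, 0.01-0.03; 60 days, 0.10-0.31; 90 days, 0.20-0.56 day.

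**6. Planned analyses against the mechanism.** Regression, matching and weighting balance characteristics measured at baseline, whereas this bias arises from what happens after baseline. The first-visit date is calendar time, not download time. Dose-response on daily or weekly use does not reassign anyone between cohorts.

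**7. Landmark check.** Among those still pregnant at week 28, classify by download before week 28. In simulation the remaining bias was within about 0.02 day, which is Monte Carlo noise. Late downloaders made up about 3-14% of the landmark usual care group at 10-30% late.

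**The case against.** Three stronger readings are tempting, and the SAP supports none of them.

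*That the plan never looks at download timing.* Section 2.3 commits to assessing days from prescription to first use, and section 1 lists time to initiation among the measures to be analysed. Combined with gestational age at the prenatal visit (Appendix A), that would go a good way towards showing whether uptake ran into the third trimester. This part of the objection stands. What remains is narrower: the measure records first activity rather than download, no breakdown by gestational age is promised, and nothing links it to cohort assignment or to a corrective analysis.

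*That the primary comparison is biased by a known amount.* No download timing is given, and the only timing fact, a prescription at an early visit, points towards the harmless end. At SD 10 the bias vanishes if downloads stop by week 36, and it is at most 0.03 day with a mean delay of 30 days. The figures near half a day need a preterm tail, or long delays, that the SAP does not state. This also stands.

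*That the bias must favour MHP.* That requires intended delay to be unrelated to gestational length. If complications prompt late downloading, the net bias could shrink or reverse.

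The early-visit statement does not dispose of the point, because it dates the prescription and not the download. The app includes a kick counter and a contraction counter (Appendix A), so late uptake is plausible, though the SAP does not show that it occurred.

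**Conclusion.** The point holds as a conditional one and is worth fixing before unblinding. Ever/never assignment without a time limit can produce a false MHP advantage in gestational age and preterm birth if a material share of downloads occurs when births are occurring and intended delay is unrelated to gestational length.

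The size cannot be determined from the SAP and may be zero. Every non-zero figure rests on assumed download timing, and the largest also on an assumed distribution of gestational age. Even the worst case in the SD-10 table, 0.25 day, is about half of the stated 0.51 day, though it would raise a nominal 5% test to 28%. The planned time-to-initiation summary is a partial check; no planned analysis is a correction.

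**What to change.** Keep ever/never download as the primary classification and add three items to the SAP.

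1. **Timing table.** Before unblinding and without outcome data, the unblinded analyst extends the planned time-to-initiation summary to gestational age at download, giving the shares after weeks 28, 32 and 36. Reporting percentages only keeps the cohort labels hidden. Appendix A lists no download or prescription date; if none is held, first recorded activity serves as proxy.
2. **One landmark sensitivity analysis** of gestational age and of preterm birth. Among those prescribed before week 28 and still pregnant then, classify by download before week 28, keep later downloaders in usual care, and report their share. The adjusted mean difference of section 3.1.1 remains the measure for gestational age.
3. **Interpretation.** State that if the ever/never and landmark estimates differ materially, immortal-time bias will be discussed as a possible explanation. The landmark should not overrule the primary result, because it is itself diluted.

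**Cost.** SAP wording, one table and one extra model for each of two outcomes.
- *Dilution:* about 3-14% of a true effect in the 10-30% late scenarios. At 14%, a true 0.51-day effect loses 0.14 × 0.51 = 0.07 day. A 28-day window from prescription would dilute more (6-27%), and a time-varying model would give a hazard-type contrast instead of a mean difference.
- *Coverage:* no information on births before week 28 (0.0-0.14% of simulated deliveries). Late prescriptions are excluded too: 4.3% if 10% are prescribed evenly over weeks 20-34, since 6/14 × 10% = 4.3%.
- *Proxy date:* app-opening and some activity records are complete only after November 2020. If 20-40% of downloaders showed activity only later, the landmark bias stayed within 0.02 day but the late share in usual care rose to 6-27%.

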1.4. Data collection

1.4.1. Eligibility Screening

Participants were included in the study if they were offered a prescription for MyHealthyPregnancy, were at least 18 years of age, pregnant, received care at UPMC, and delivered at a UPMC hospital.

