1.5. Sample Size Justification

Due to the observational nature of the study and recruitment context, it was not possible to predetermine the sample size based on statistical power for estimating the primary and secondary outcomes. Instead, all participants who met the inclusion criteria between September 2019 and February 2022 were included. The final sample has 12,344 deliveries, divided between the MHP and usual care cohorts (with 7147 in one and 5197 in the other, with their identities currently blinded). This represents about 12,287 different participants (we only have information about the percent of multiple deliveries for participants who downloaded the app, 0.464%). Given the sample sizes in the two cohorts, there is 80% power to detect an effect size of 0.051 days. Assuming that the outcomes are normally distributed with a standard deviation of 10 days (1), the study has 80% power to detect a 0.51 day difference in gestational age at birth between the cohorts.

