Some collected covariates are specific to this dataset. One is hospital location, which may capture differences in resources, practices, and patient populations. The second is the date of the first visit recorded in Epic, which may capture factors like access to care or social conditions (e.g., the pandemic). We will include hospital location as a variable in all models. We will not include date of first visit as it might be correlated with ones that affect the effectiveness of the app over time.

Residual plots will be used to evaluate the models for heteroskedasticity and the need for using robust standard errors, in order to allow for violations in the assumption that observations are independent and identically distributed (8).

Differences between the cohorts will be described using adjusted mean differences and p-values. Results will be considered significant at $p < 0.05$.

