Appendix A

Covariates and Outcomes

Variable Name in EHR	Description	Variable type
PATIENT_ID	ID for each patient not related to patient information	ID
MOM_AGE	Mother's age at time of delivery	Baseline covariate
FINANCIAL_CLASS	Payor at time of delivery from Medipac (insurance level, might be like coverage) (i.e. name like 'UPMC HEALTH NETWORK', 'MED PLUS', 'BEST HEALTH CARE', etc)	Baseline covariate
HOSP_ROLLUP_GROUPING1	Payor at time of delivery from Medipac (insurance type) (i.e. specifies type of UPMC insurance, examples include 'UPMC Commercial', 'Other MA Managed', 'Other Commercial', etc)	Baseline covariate
HOSP_ROLLUP_GROUPING2	Medicare, Medicaid, Self-pay, or Commercial Insurance	Baseline covariate
HPFLAG	Payor at time of delivery from Medipac (UPMC Health Plan Member flag, 1= has UPMC Health Plan, 0=Doesn't have it)	Baseline covariate
PT_ZIP	Patient zipcode	Baseline covariate
AD_ZIP_4	Patient zipcode, location extension (+4)	Baseline covariate
ADI_NATRANK	Area deprivation index, national ranking (0 most deprived, 100 least deprived)	Baseline covariate
RACE	Race, as reported through UPMC	Baseline covariate
MOM_HEIGHT	mother's height at time of delivery (cm)	Baseline covariate
OB_GRAVIDITY	Number of pregnancies (includes current pregnancy, so if it's their first pregnancy, this will be a 1)	Baseline covariate
OB_PARITY	Number of previous deliveries (will be 0 if it's their first pregnancy)	Baseline covariate
OB_FULL_TERM	Number of previous full term pregnancies	Baseline covariate
OB_PREMATURE	Number of previous premature deliveries (prior to 37 gestational weeks)	Baseline covariate
OB_ABORTIONS	Number of previous abortions, including therapeutic/spontaneous abortions	Baseline covariate
OB_LIVING	Number of previous live deliveries	Baseline covariate
OB_SPONTANEOUS_AB	Number of previous miscarriage/spontaneous abortions	Baseline covariate
OB_THERAPEUTIC_AB	Number of previous therapeutic abortions	Baseline covariate
PREGRAVID_WEIGHT	mother's pre-pregnancy weight (kg)	Baseline covariate
GESTAGE_ATVISIT_DAYS	This is the gestational age of the pregnancy at the time of prenatal visit. Calculated using the estimated delivery date ((280-(EPISODE.OB_WRK_EDD_DT-pat_enc.contact_date))).	Baseline covariate
PREGSTART_OBESE	Obese BMI at first prenatal visit (binary variable)	Baseline covariate
PREGSTART_MORBIDOBSE	Morbidly obese BMI at first visit (binary variable)	Baseline covariate

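### Gestational age at entry is not limited by eligibility and not pre-specified as a covariate, although gestational age at birth, preterm birth and visit counts depend on it

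*SAP*

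**What the plan says.** Section 1 of the SAP describes entry this way: "Prescriptions were offered to pregnant people by their care team at an early prenatal visit at UPMC". Section 1.3 says the same, and neither gives a week. The inclusion rule in section 1.4.1 covers participants who were "offered a prescription for MyHealthyPregnancy, were at least 18 years of age, pregnant, received care at UPMC, and delivered at a UPMC hospital". Section 1.5 states that everyone meeting the inclusion criteria in the study period was included.

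Section 3.1.1 lists ten known confounders of preterm birth, from previous preterm birth to tobacco use. Gestational age at entry is not among them, nor is it named for any secondary outcome in section 3.1.2. For the number of prenatal appointments attended, that section names no confounder at all.

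Appendix A types GESTAGE_ATVISIT_DAYS as a baseline covariate: "This is the gestational age of the pregnancy at the time of prenatal visit". It does not say which visit.

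On timing, the text of section 3.1.1 discusses only the calendar date: "We will not include date of first visit". Section 3.1.5 brings that date back as a sensitivity analysis.

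**The concern.** A pregnancy first seen at week w can be in the data only if it was still continuing at week w. Early entrants contribute the whole distribution of gestational age at birth; late entrants contribute a distribution with its lower end cut off. This left truncation acts at prescription in both cohorts, and would remain even if every download happened on the day of prescription. It does no harm if the download share is the same at every entry time. If late entrants download less often (or more often), the two cohorts mix truncated and untruncated pregnancies in different proportions, and a difference in the primary outcome and in preterm birth appears without any effect of the app.

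The visit count is exposed more directly, because someone who enters late has fewer visits left to attend.

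Section 3.1.1 reports two models per outcome. As listed, the literature-only model has no term for entry time. The second can gain one only through the 10% change-in-estimate screen, and the propensity model only through the conditional rule in section 3.1.5. The calendar date of the first visit is no substitute: it records when in the study period a person came, not how far along the pregnancy was.

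**Working it through.** **The plan's own figure.** Inputs: "The primary and secondary outcomes will be evaluated at the 5% significance level" (section 3.1; two-sided assumed); cohorts of 7147 and 5197 (section 1.5); "Assuming that the outcomes are normally distributed with a standard deviation of 10 days".

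(1.960 + 0.842) × √(1/5197 + 1/7147) = 2.802 × 0.01823 = 0.0511; times 10 days = 0.51 day.

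The stated 0.51 day is reproduced. (Section 1.5 also says "there is 80% power to detect an effect size of 0.051 days"; that value works only as a standardized effect, not in days.) At an SD of 13.7 days the detectable difference is 0.0511 × 13.7 = 0.70 day.

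**How far truncation moves the mean.** The SAP gives no entry-time distribution, so this is bracketed by assumption. The shift is E[T | T > w] − E[T], with T the gestational age at birth.

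- Normal, SD 10 days, mean 280 assumed: under 0.001 day at 34 weeks and 0.08 day at 36 weeks.
- Left-tailed distribution with 10% preterm, SD 13.8 days (simulated):

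| Entry week | Shift in mean (days) | Bias if late share differs by 10 points (days) | Share difference needed for 0.70 day |
|---|---|---|---|
| 20 | 0.01 | 0.001 | not reachable |
| 24 | 0.06 | 0.006 | not reachable |
| 28 | 0.27 | 0.03 | not reachable |
| 32 | 1.00 | 0.10 | 0.70/1.00 = 70 points |
| 34 | 1.79 | 0.18 | 0.70/1.79 = 39 points |
| 36 | 2.95 | 0.29 | 0.70/2.95 = 24 points |

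The shift is nearly flat to about 28 weeks and then steepens, so a single linear term in entry time would remove only part of the bias.

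**Scenarios with no app effect.** Assumptions: a share L of 3 to 10% enters after 28 weeks; 60% of earlier entrants download, against p = 15 to 45% of late entrants. A left-tailed mixture with SD about 13.7 days was simulated; in it, entrants after 28 weeks have a mean gestation about 1.8 days longer than earlier entrants.

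Late share in MHP = Lp / [Lp + 0.60(1−L)]. Late share in usual care = L(1−p) / [L(1−p) + 0.40(1−L)].

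- L = 3%, p = 45%: 2.3% against 4.1%, 1.8 points; × 1.8 days = 0.03 day.
- L = 5%, p = 30%: 2.6% against 8.4%, 5.9 points; × 1.8 = 0.11 day.
- L = 10%, p = 15%: 2.7% against 19.1%, 16.4 points; × 1.8 = 0.30 day.

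Full simulation agrees: about 0.03 to 0.31 day, with MHP shorter, and preterm birth about 0.1 to 0.5 percentage points higher in MHP. With a normal outcome and SD 10, the largest value is about 0.09 day.

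Against the detectable difference at the matching SD, the left-tailed cells are 0.03/0.70 = 4%, 0.11/0.70 = 16% and 0.30/0.70 = 43%; the worst normal cell is 0.09/0.51 = 18%.

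**Visit count.** Under the same scenarios and an assumed schedule (every 4 weeks to week 28, every 2 weeks to week 36, then weekly), the spurious difference is 0.1 to 1.1 visits in favour of MHP.

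**The case against.** A gestational window may stand in the protocol, which is not at hand. Eligibility requires a prescription offer, and the SAP says twice that the offer came early, so the sections do not contradict each other. No late entrant is reported, and the 3 to 10% share is an assumption. All of that stands. It limits what can be said about size, but the choice of covariates belongs to the SAP and is still open.

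It can also be said that the plan already has routes for the variable. The confounder list in section 3.1.1 is not declared exhaustive; the 10% screen can be triggered by the likelihood of downloading as well as by the outcome; and section 3.1.5 admits to the propensity model any baseline confounder related to both treatment and outcome, with no 10% threshold. Where the bias is real, these rules lean towards inclusion. So a reader who inferred that the variable is missing, or that the 10% screen is its only way in, would be wrong. What remains is that every route is conditional and that nothing places it in the literature-only model.

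A reader might also infer that late entrants bring guaranteed long gestations. They do not: only survival past the entry week is assured, and entry at 28 weeks still allows a very preterm birth. Nor do the figures support a bias above half of what the study can detect. That reading sets the worst left-tailed scenario (SD 13.7) against a detectable difference computed at SD 10.

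**Conclusion.** The point holds as a gap in pre-specification. The SAP sets no gestational-age limit on entry, names gestational age at entry as a confounder for no outcome, and leaves a collected covariate to conditional rules. The mechanism follows from the design; its size and sign do not follow from anything in the document. Under the assumed scenarios the bias in the primary outcome is about 0.03 to 0.3 day with a left-tailed distribution, or at most about 0.1 day under the SAP's normal SD of 10. That is a minority of the detectable difference in every cell, and it would not shrink with more data. If late entrants are mainly high-risk transfers, the sign could reverse.

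It might seem to follow that the main analysis set should be cut at a fixed week. The document gives no basis for any particular cut-off, and excluding late entrants changes the population described, so such a restriction belongs in a sensitivity analysis.

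**What to change.** 1. In Appendix A, state which visit GESTAGE_ATVISIT_DAYS records (first prenatal visit, prescription visit or other). Gestational age at prescription is not listed separately, so this must be settled first.
2. In sections 3.1.1 and 3.1.2, pre-specify gestational age at the first prenatal or prescription visit in every outcome model, including the literature-only model. In section 3.1.5, pre-specify it in the propensity model used for matching and weighting. Use a flexible form, such as a spline or categories that separate late entry.
3. Add a sensitivity analysis restricted to patients who entered before a stated gestational age that matches the description of an early prenatal visit, fixed before the cohort labels are revealed.
4. Keep the all-comers main analysis set and the existing decision on the calendar date of the first visit.

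The cost is a few degrees of freedom among 12,344 deliveries, one extra sensitivity analysis, and confirmation of one variable definition.
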